## 5.1 Statistical Methods

### 5.1.1 Hypotheses and Statistical Methods for Primary Objectives

No hypotheses will be tested.

For descriptive purposes, the statistics presented on Table 5.1 will be produced.

### 5.1.1.1 Hypotheses

### 5.1.1.2 Statistical Methods

Disposition, demographics, medical history and concomitant medications data will be summarized using counts and percentages.

#### *Safety*

Safety results will be analyzed for participants in the safety analysis set (SafAS) who at least received one of the vaccines. The main parameters will be described with 95% CI. At least the following parameters will be presented by group after each/any vaccination(s) as applicable:

- Immediate unsolicited systemic AEs
- Solicited injection site reactions and solicited systemic reactions occurring within 7 days after the day of injection (D0 to D7) according to occurrence (presence), time of onset, intensity (Grade 1, Grade 2, or Grade 3), number of days of occurrence (presence) and action taken
- Unsolicited AEs occurring within 30 days after injection by system organ class (SOC) and PT, relationship, intensity, time of onset, and duration
- All SAEs that occur throughout the study by SOC and PT, relationship and seriousness criteria
- All AESIs that occur throughout the study by SOC and PT and relationship

#### *Immunogenicity - Stage I toddlers*

The point estimates and their 95% CI of the following parameters will be presented for each group before and 1-month post-vaccination for each pneumococcal serotype specific IgG concentrations:

- GM of serotype specific IgG concentrations
- GM of IgG concentrations ratio (post- / pre-vaccination)

In addition, the difference between any SP0202 group (Group 1 to 3) and the Prevnar 13 group (Group 4) will be presented in terms of:

- GM ratio of serotype specific IgG concentrations between groups (SP0202/Prevnar 13) and 95% CI at 1-month post-vaccination

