Following DMC recommendations after Stage I early safety data review (ESDR), any SP0202 formulation may be excluded from entering Stage II of the study if considered not adequate for further evaluation in infants. In such a case, the number of groups to entered Stage II will be adjusted accordingly and the planned sample size in each selected group will be kept.

An Interactive Response Technology (IRT) will be used to assign participant numbers and study group at each clinical site.

Over the study period of Stage I (Group 1 to 4), toddlers will attend 2 planned visits at D0 and D30. Two blood samples (BL) of 6 mL each will be collected for the assessment of the immunogenicity of the 3 SP0202 formulations, Prevnar 13 and Pentacel: before injection of PCV (BL0001) at D0 (Visit 1 [V01]) and 1 month after PCV injection (BL0002) at D30 (V02).

Over the study period of Stage II (Group 5 to 8), infants will attend 6 planned visits at D0, D60, D120, D150, D300-390, and D330-420. Overall, 3 or 4 BL will be collected for the assessment of the immunogenicity of the 3 SP0202 formulations, Prevnar 13 and pediatric vaccines: before injection of PCV (BL0001; 3 mL) at D0 (V01)\*, 1 month after PCV Dose 3 (BL0002; 6 mL) at D150 (V04), before PCV Dose 4 (BL0003; 6 mL) at D300 (V05), and 1 month after PCV Dose 4 (BL0004; 6 mL) at D330 (V06).

The study vaccine-related immunogenicity assessments will involve both the measurement of serotype specific IgG concentrations and of OPA titers. IgG concentrations for all pneumococcal serotypes included in each of the SP0202 formulations and Prevnar 13 will be measured in all participants. The evaluation of the IgG concentrations will be made using the international standard reference serum 007sp that includes assignment for all serotypes included in SP0202. OPA will be measured in all available samples from Stage 1 and on a subset of Stage 2 samples.

The immunogenicity of the pediatric vaccines administered concomitantly with the study vaccines will be assessed using standard assays for the respective antigens.

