**Table 5.1: Descriptive statistics produced**

Baseline characteristics and follow-up description	Categorical data	Number of participants. Percentage of participants.
	Continuous data	Mean, standard deviation, quartiles, minimum, and maximum.
Clinical safety results	Categorical data	Solicited: Number and percentage (95% CIs) of participants. Unsolicited: Number and percentage (95% CIs) of participants, and number of events.
Immunogenicity results	Categorical data (seroprotection, cutoff, thresholds)	Number and percentage (95% CIs) of participants.
	Continuous data (titer / data)	Log10: Mean and standard deviation. Anti-Log10 (work on Log10 distribution, and anti-Log10 applied): Geometric mean, 95% CI of the geometric mean, quartiles, minimum, and maximum. Graphical representation by Reverse Cumulative Distribution Curve (RCDC). Boxplots and Forest plots.

The CI for the single proportion will be calculated using the exact binomial method (Clopper-Pearson method, quoted by Newcombe (2)), ie, using the inverse of the beta integral with SAS®.

For immunogenicity results, assuming that Log10 transformation of the titers / concentrations follows a normal distribution, at first, the mean and the 95% CI will be calculated on Log10 (titers / data) using the usual calculation for normal distribution (using Student's t distribution with n-1 degree of freedom), then antilog transformations will be applied to the results of calculations, in order to provide geometric means (GMs) and their 95% CI.

CIs of the difference of proportions between 2 groups will be computed using the Wilson Score method without continuity correction. CIs of ratio of GMTs / GMCs between 2 groups will be computed from the difference in means of log10 transformed titers/concentrations between 2 groups with normal approximation.

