**Table 5.2: Summary of statistical analyses for immunogenicity analysis of primary endpoints**

Endpoint	Visit and Group	Description
Serotype specific pneumococcal IgG concentration for each of the 21 serotypes	V01 and V02 - Toddlers V01*, V04, V05 and V06 - Infants	IgG GMC and 95% CI, corresponding Forest Plot
	V02/V01 - Toddlers V04/V01*, V06/V05 - Infants	IgG GM ratio (post/pre) and 95%CI
	V01 and V02 - Toddlers V01*, V04, V05 and V06 - Infants	Proportion of participants with concentration $\geq 0.35 \mu\text{g/mL}$ and 95% CI, corresponding Forest Plot
	V02 - Toddlers V04 and V06 - Infants	IgG GMC ratio and 95% CI between any SP0202 group and Prevnar 13 (ie, Group 1/Group 4, Group 2/Group 4, Group 3/ Group 4; Group 5/Group 8, Group 6/Group 8, Group 7/Group 8) and corresponding Forest Plot
	V04 and V06 - Infants	IgG GMC ratio and 95% CI between SP0202 groups (ie, Group 6/Group 5, Group 7/Group 5 and Group 7/Group 6) and corresponding Forest Plot
	V04 - Infants	Difference of proportion of participants with concentration $\geq 0.35$ and 95% CI between any SP0202 group and Prevnar 13 (ie, Group 5 - Group 8, Group 6 - Group 8 and Group 7 - Group 8) and between SP0202 groups (ie, Group 6 - Group 5, Group 7 - Group 5 and Group 7 - Group 6), and corresponding Forest Plot
	V01 and V02 - Toddlers V04, V05 and V06 - Infants	IgG concentration RCDC
	V01 and V02 - Toddlers V04, V05 and V06 - Infants	IgG concentration boxplot

\*Pre-dose 1 BL is done only for participants enrolled before protocol amendment V5.0

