##### **5.1.2.2.1 Stage I toddlers**

###### ***Immunogenicity of SP0202 or Prevnar 13***

The point estimates and their 95% CI of the following parameters will be presented for each group before and 1-month post-vaccination for pneumococcal serotype specific OPA titers:

- GM of serotype specific titers, GM of titers ratio (post- / pre-vaccination)
- Percentage of participants with a serotype specific titer above or equal to LLOQ

In addition, the difference between any SP0202 group (Group 1 to 3) and the Prevnar 13 group (Group 4) will be presented in terms of:

- GM ratio between groups (SP0202/Prevnar 13) and 95% CI at 1-month post-vaccination

Several graphical representations will be used such as: RCDCs of individual concentrations and Forest plots of GMTs for all serotypes.

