**Table 5.3: Summary of Statistical analyses for immunogenicity analysis of secondary endpoints**

Endpoint	Visit and Group	Description
Serotype specific pneumococcal OPA titer for each of the 21 serotypes	V01 and V02 - Toddlers V04, V05 and V06 - Infants OPA subset	OPA GMT and 95% CI, corresponding Forest Plot
	V02/V01 - Toddlers V06/V05 - Infants OPA subset	OPA GM ratio (post/pre) and 95% CI
	V01 and V02 - Toddlers V04, V05 and V06 - Infants OPA subset	Proportion of participants with titer $\geq$ LLOQ and 95% CI
	V02 - Toddlers V04 and V06 - Infants OPA subset	OPA GMT ratio and 95% CI between any SP0202 group and Prevnar 13 (ie, Group 1/Group 4, Group 2/Group 4, Group 3/ Group 4; Group 5/Group 8, Group 6/Group 8, Group 7/Group 8) and corresponding Forest Plot
	V04 and V06 - Infants OPA subset	OPA GMT ratio and 95% CI between SP0202 groups (ie, Group 6/Group 5, Group 7/Group 5 and Group 7/Group

\* Not applicable from protocol Version 5.0

† Immunogenicity to ENGERIX-B will be presented according to the number of doses received

		6), and corresponding Forest Plot
	V01 and V02 - Toddlers V04, V05 and V06 - Infants OPA subset	OPA titer RCDC
Anti-tetanus and anti-diphtheria	V01 and V02 - Toddlers V01* and V04 - Infants	GMC and 95% CI
		RCDC
		Proportion of participants with concentration $\geq 0.10$ IU/mL and 95% CI
	V01* and V04 - Infants	Proportion of participants with concentration $\geq 1.0$ IU/mL and 95% CI
Anti-PT, anti-FHA, anti-PRN and anti-FIM	V01 and V02 - Toddlers	GMC and 95% CI
	V01* and V04 - Infants	RCDC
	V02/V01 - Toddlers	Proportion of participants with pertussis vaccine response from pre to post vaccination and 95% CI
Anti-PRP	V01 and V02 - Toddlers V04 - Infants	GMC and 95% CI
		Proportion of participants with concentration $\geq 0.15$ $\mu$ g/mL and 95% CI
		Proportion of participants with concentration $\geq 1.0$ $\mu$ g/mL and 95% CI
		RCDC
Anti-Hepatitis B	V04 - Infants	GMC and 95% CI
		RCDC
		Proportion of participants with concentration $\geq 10$ IU/mL and 95% CI
		Proportion of participants with concentration $\geq 100$ IU/mL and 95% CI
Anti-Rotavirus	V01*, V04 - Infants	GMC and 95% CI
		RCDC
Anti-measles	V06 - Infants	GMC and 95% CI
		RCDC
		Proportion of participants with concentration $\geq 255$ mIU/mL and 95% CI
Anti-mumps	V06 - Infants	GMC and 95% CI
		RCDC
		Proportion of participants with concentration $\geq 10$ mumps Ab U/mL and 95% CI

Anti-rubella	V06 - Infants	GMC and 95% CI
		RCDC

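### The Stage I SP0202/Prevnar 13 ratios at V02 ignore baseline antibody; a supportive baseline-adjusted ratio could be more precise with about 31 toddlers per group

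*SAP*

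**What the plan says.** IgG and OPA are toddler endpoints at baseline and at 30 days (SAP 4.2.1 and 4.2.2.1). SAP 3.1 adds that "OPA will be measured in all available samples from Stage 1".

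The between-group comparisons use V02 only:

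- IgG: "GM ratio of serotype specific IgG concentrations between groups (SP0202/Prevnar 13) and 95% CI at 1-month post-vaccination" (SAP 5.1.1.2), listed in Table 5.2 as "IgG GMC ratio and 95% CI between any SP0202 group and Prevnar 13".
- OPA: "GM ratio between groups (SP0202/Prevnar 13) and 95% CI at 1-month post-vaccination" (SAP 5.1.2.2.1), listed in Table 5.3 as "OPA GMT ratio and 95% CI between any SP0202 group and Prevnar 13".

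The text after Table 5.1 says that the intervals for these ratios are "computed from the difference in means of log10 transformed titers/concentrations between 2 groups with normal approximation". Protocol 12.1.1.2 gives the same method. No covariate is named.

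V01 appears only in output by group: GMCs and GMTs, post/pre geometric mean ratios with 95% CIs, proportions above a threshold, reverse cumulative distribution curves and, for IgG, boxplots. The complementary analyses in SAP 5.1.3 add no adjusted contrast. The subgroup and V01-sample analyses there concern infants, and the Stage I heatmaps use post-vaccination values.

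All analyses are descriptive (protocol 12.1.1.1, SAP 5.1.1). SAP 5.5 anticipates 31 evaluable toddlers per group.

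**The concern.** Stage I is the smallest comparison in the trial. It is also the one where baseline may carry most information, because every toddler has had three doses of Prevnar 13. The V01 value precedes the randomised injection, so it can be used as a covariate without risk to the comparison. If V01 and V02 antibody levels are correlated within a serotype, the planned ratio leaves explainable variation in its standard error. At stake is precision only: ratios at this sample size will be imprecise, and data already collected might narrow them.

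**Working it through.** **Sample size.** 35 per group with 10% dropout gives 35 × 0.90 = 31.5, rounded down to 31. This reproduces the figure in SAP 5.5.

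**Assumed inputs.** The documents give no log10 SD, no V01-V02 correlation of log10 values (rho) and no expected number without V01. I take rho from 0 to 0.7, and k = 0 to 3 toddlers per group lacking V01. Missing V01 is possible: protocol 5.1.4 lets a toddler continue without BL0001, PPAS1 and FAS1 do not require V01 (SAP 5.2.1, 5.2.2), and missing values are not imputed (SAP 5.3.2).

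**Formulas (log10 half-widths).**

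- Planned: 1.96 × SD × √(2/31).
- Adjusted, with m = 31 − k per group: t(0.975, 2m−3) × SD × √(2/m) × √[(1−rho²)(1 + 1/(2m−4))].

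SD cancels from the relative change. At k = 0 and rho = 0.5, t(59) = 2.001, so the width ratio is (2.001/1.96) × √0.75 × √(1 + 1/58) = 0.892, a reduction of 10.8%.

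**Change in log-scale width against the planned interval.**

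| Lacking V01 per group | rho 0 | rho 0.3 | rho 0.5 | rho 0.7 | Break-even rho |
|---|---|---|---|---|---|
| 0 | +3.0% | -1.8% | -10.8% | -26.5% | 0.24 |
| 1 | +4.8% | 0.0% | -9.3% | -25.2% | 0.30 |
| 2 | +6.7% | +1.8% | -7.6% | -23.8% | 0.35 |
| 3 | +8.7% | +3.7% | -5.9% | -22.4% | 0.39 |

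**On the ratio scale.** At an assumed log10 SD of 0.45, the planned half-width is 1.96 × 0.45 × √(2/31) = 0.224, so the interval multiplies and divides the ratio by 1.68. Adjusted at rho 0.5, the factor is 1.58 with none missing, and 1.60, 1.61 or 1.63 with 1, 2 or 3 missing. Over SDs of 0.3 to 0.6, the planned factor runs from 1.41 to 1.99 and the adjusted factor (rho 0.5, none missing) from 1.36 to 1.85.

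**Critical value.** These figures compare the SAP's normal-based interval with a t-based one. With t on both sides and none missing, the changes are +0.9%, -3.8%, -12.6% and -27.9%, with break-even near rho 0.13.

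**Dividing two planned post/pre ratios.** With equal V01 and V02 SDs and no missing V01, this interval is √[2(1−rho)] times the width of the planned V02 ratio: 1.183, 1.000 and 0.775 at rho 0.3, 0.5 and 0.7. It is 18% wider at 0.3, equal at 0.5 and 22.5% narrower at 0.7, so it does not replace ANCOVA.

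**Simulation.** In 10,000 trials for each of 16 settings (k 0 to 3, the four rho values, V01 missing at random), coverage was 94.2-95.0% for the planned interval and 94.6-95.4% for ANCOVA. Width changes were within 0.2 percentage points of the formula. Further simulations with unequal slopes, unequal SDs and a floor at the LLOQ left ANCOVA unbiased, with coverage of 94.5-95.5% and intervals 3-11% narrower.

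**The case against.** The strongest objection is that nothing is wrong. The planned interval is valid, the analyses are descriptive, and the Stage I gate to infants is a safety review. V01 is already reported by group, so a reader can see a baseline imbalance. All of this is right, and it is why the point is optional.

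The benefit also rests on assumed inputs. Across the table it runs from 8.7% wider to 26.5% narrower, so even its sign is unknown for a given serotype. That stands.

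Part of the tabulated change comes from using t instead of 1.96. That is correct, but it understates the gain from adjustment.

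For the 8 added serotypes, the Prevnar 13 group receives no matching antigen, and many V01 values may lie below the LLOQ. Slopes and SDs may then differ between groups. The further simulations show that such conditions do not spoil validity. The expectation of little gain for these serotypes remains a judgement.

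The adjusted estimate would differ from the lead in covariate, critical value and, where V01 is missing, population. A width difference could then not be credited to baseline alone. That is fair, and it is why the number of toddlers must be shown beside each estimate.

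Finally, the protocol synopsis plans an unblinded Stage I analysis through V02. Whether it has already happened cannot be settled from the documents.

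**Conclusion.** The point holds as an optional improvement. No planned Stage I between-group contrast uses V01, although IgG and OPA are measured then. The planned ratios are unbiased and their intervals keep close to nominal coverage, so they should stay. With all 31 toddlers per group having V01, adjustment would narrow the log-scale interval by about 11% at rho 0.5 and 26.5% at rho 0.7, do almost nothing at 0.3, and widen it by 3% at 0. A few missing V01 samples reduce the gain and raise the break-even correlation to between 0.30 and 0.39. These sizes rest on assumed correlations and missing counts. The greater promise for the 13 shared serotypes is inferred from the toddlers' earlier vaccination. No stated decision depends on these ratios.

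**What to change.** In SAP 5.1.1.2 and 5.1.2.2.1 and in Tables 5.2 and 5.3, add a supportive analysis for each serotype and each SP0202/Prevnar 13 pair:

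- Fit an ANCOVA of log10 V02 on group and log10 V01 to the two groups compared, using toddlers with both samples, with a t-based 95% CI.
- Set V01 and V02 values below the LLOQ to LLOQ/2, as the SAP already does for GMCs and GMTs.
- Keep the planned unadjusted ratio on all evaluable toddlers as the lead estimate, and print the number of toddlers beside each estimate.
- If Stage I was already unblinded, label the adjusted analysis post hoc.

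The cost is SAP wording and programming: 21 serotypes × 3 pairs × 2 assays = 126 ratios per analysis set, or 252 for both PPAS1 and FAS1. Limiting it to the 13 shared serotypes gives 13 × 3 × 2 = 78 per set. No new samples, assays or visits are needed. The downsides are a slightly wider interval where the correlation is low, and the loss of toddlers without BL0001 from the adjusted estimate.

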#### *Immunogenicity - Stage II infants*

The point estimates and their 95% CI of the following parameters will be presented for each group for each pneumococcal serotype specific IgG concentrations when applicable:

- Percentage of participants with a PD3 and PD4 serotype specific IgG concentrations  $\geq 0.35 \mu\text{g/mL}$
- GM of serotype specific IgG concentrations / titers (pre-dose 1\* as applicable, PD3, pre-dose 4, PD4)

- GM of serotype specific IgG concentrations / titers ratio (PD3/pre-dose 1\* as applicable, PD4/pre-dose 4)

In addition, difference between any SP0202 group (Group 5 to 7) and the Prevnar 13 group (Group 8) and between SP0202 groups will be presented in terms of:

- Differences of percentages of participants with serotype specific IgG concentration  $\geq 0.35 \mu\text{g/mL}$  and 95% CI at PD3
- GM ratio of serotype specific IgG concentrations between groups and 95% CI at PD3 and PD4

Several graphical representations will be used such as: RCDCs of individual concentrations, Boxplots of the  $\log_{10}$  concentrations and Forest plots of GMCs for all serotypes.

\*Pre-dose 1 BL is done only for participants enrolled before protocol amendment V5.0

**Table 5.2: Summary of statistical analyses for immunogenicity analysis of primary endpoints**

Endpoint	Visit and Group	Description
Serotype specific pneumococcal IgG concentration for each of the 21 serotypes	V01 and V02 - Toddlers V01*, V04, V05 and V06 - Infants	IgG GMC and 95% CI, corresponding Forest Plot
	V02/V01 - Toddlers V04/V01*, V06/V05 - Infants	IgG GM ratio (post/pre) and 95%CI
	V01 and V02 - Toddlers V01*, V04, V05 and V06 - Infants	Proportion of participants with concentration $\geq 0.35 \mu\text{g/mL}$ and 95% CI, corresponding Forest Plot
	V02 - Toddlers V04 and V06 - Infants	IgG GMC ratio and 95% CI between any SP0202 group and Prevnar 13 (ie, Group 1/Group 4, Group 2/Group 4, Group 3/ Group 4; Group 5/Group 8, Group 6/Group 8, Group 7/Group 8) and corresponding Forest Plot
	V04 and V06 - Infants	IgG GMC ratio and 95% CI between SP0202 groups (ie, Group 6/Group 5, Group 7/Group 5 and Group 7/Group 6) and corresponding Forest Plot
	V04 - Infants	Difference of proportion of participants with concentration $\geq 0.35$ and 95% CI between any SP0202 group and Prevnar 13 (ie, Group 5 - Group 8, Group 6 - Group 8 and Group 7 - Group 8) and between SP0202 groups (ie, Group 6 - Group 5, Group 7 - Group 5 and Group 7 - Group 6), and corresponding Forest Plot
	V01 and V02 - Toddlers V04, V05 and V06 - Infants	IgG concentration RCDC
	V01 and V02 - Toddlers V04, V05 and V06 - Infants	IgG concentration boxplot

\*Pre-dose 1 BL is done only for participants enrolled before protocol amendment V5.0

### **5.1.2 Hypotheses and Statistical Methods for Secondary Objectives**

#### **5.1.2.1 Hypotheses**

#### **5.1.2.2 Statistical Methods**

No hypotheses were tested. For descriptive purposes, the statistics presented on Table 5.1 will be produced.

##### **5.1.2.2.1 Stage I toddlers**

###### ***Immunogenicity of SP0202 or Prevnar 13***

The point estimates and their 95% CI of the following parameters will be presented for each group before and 1-month post-vaccination for pneumococcal serotype specific OPA titers:

- GM of serotype specific titers, GM of titers ratio (post- / pre-vaccination)
- Percentage of participants with a serotype specific titer above or equal to LLOQ

In addition, the difference between any SP0202 group (Group 1 to 3) and the Prevnar 13 group (Group 4) will be presented in terms of:

- GM ratio between groups (SP0202/Prevnar 13) and 95% CI at 1-month post-vaccination

Several graphical representations will be used such as: RCDCs of individual concentrations and Forest plots of GMTs for all serotypes.

###### ***Immunogenicity of concomitant vaccine***

The point estimates and their 95% CI of the following parameters will be presented for each group before and 1-month post-vaccination for Pentacel antigens:

- GM of concentrations / titers for all antigens
- Percentage of participants with concentration / titer above the predefined threshold, including those defining seroprotection
- Vaccine response rate for pertussis (PT, FHA, PRN, and FIM) antigens

RCDCs of individual concentrations / titers will be presented for all serotypes / antigens.

##### **5.1.2.2.2 Stage II infants**

###### ***Immunogenicity of SP0202 or Prevnar 13***

The point estimates and their 95% CI of the following parameters will be presented for each group in the OPA subset and for each pneumococcal serotype specific OPA titers:

- Percentage of participants with a PD3 and PD4 serotype specific titer above or equal to LLOQ
- GM of serotype specific titers (PD3, pre-dose 4, PD4)
- GM of serotype specific titers ratio (PD4/pre-dose 4)

In addition, the difference between any SP0202 group (Group 5 to 7) and the Prevnar 13 group (Group 8) and between SP0202 groups will be presented in terms of:

- GM ratio between groups and 95% CI at PD3 and PD4

Several graphical representations will be used such as: RCDCs of individual concentrations and Forest plots of GMCs for all serotypes.

***Immunogenicity of concomitant vaccines:***

The point estimates and their 95% CI of the following parameters will be presented for each group for concomitant vaccines (Pentacel, ENGERIX-B, RotaTeq, M-M-RII, and VARIVAX) antigens:

- GM of concentrations / titers for all antigens (at pre-Dose 1\* for RotaTeq, Diphtheria, Tetanus and Pertussis antigens; at PD3 for ENGERIX-B†, RotaTeq, and Pentacel; at PD4 for M-M-RII and VARIVAX)
- Percentage of participants with concentrations / titers above predefined thresholds, including those defining seroprotection (at PD3 and PD4 as applicable)

RCDCs of individual concentrations / titers will be presented for all serotypes / antigens.

As Engerix-B vaccine was not mandatory from protocol amendment V5.0 and therefore number of doses administered will differ according to countries, the level of antibodies measured will be analyzed according to number of doses of Hepatitis-B vaccine received before and during the study.

\* Pre-dose 1 BL is done only for participants enrolled before protocol amendment V5.0

